**Unique Protocol ID: 23-1367**

**BACKGROUND**

The radial artery (RA) is considered to be the vascular access of choice to perform percutaneous coronary intervention (PCI). (1, 2) The main advantage of conventional radial access (CRA) compared to femoral artery access is the reduction in major vascular complications and major bleeding. (3) This benefit reduces the rate of major adverse events and cardiovascular mortality. Outstanding randomized studies have confirmed the superiority of RA associated with a lower rate of vascular complications and mortality. (4, 5) The MATRIX study (Minimizing adverse haemorrhagic events by transradial access site and systemic implementation of angiox) demonstrated lower global mortality at 30 days with RA in patients with Acute Coronary Syndrome (ACS) (1.65 vs. 2.2%,  $p=0.045$ ). (6) This reduction was also demonstrated in the rate of compound events of death, myocardial infarction (MI), cerebrovascular event, and BARC type 3 or 5 (9.8% vs. 11.7%,  $p=0.0092$ ). (6, 7) In the RIVAL study (Radial versus femoral Access for percutaneous coronary intervention) the effectiveness of RA was similar to femoral access, with a lower rate of local vascular complications. (8) A subsequent analysis of the same study documented a greater benefit of RA in reducing net clinical adverse events and mortality in patients with AMI (Acute Myocardial Infarction) and elevation of the ST segment (STEMI). (9) The combination of events of death, MI, cerebrovascular event, or major bleeding was 4.19% with RCA and 8.18% with femoral access ( $p<0.001$ ) in patients with STEMI.

Distal radial access (DRA) has emerged as an alternative to CRA in PCI. (10) Compared to CRA access, RDA is associated with a lower rate of radial artery occlusion (RAO) and hematoma (10);

**SALUD**  
SECRETARÍA DE SALUD

**Instituto Nacional de Cardiología Ignacio Chávez**  
*Renacimiento de la Excelencia*

however, it requires more time for radial artery cannulation, more puncture attempts, and a higher rate of conversion to femoral. (10, 11)

There is no evidence that RDA is superior to CRA in patients with STEMI undergoing interventional treatment in relation to net adverse clinical events.

### **STATEMENT OF THE PROBLEM**

Randomized studies have shown that DRA is associated with lower local complication rates than CRA access, primarily reducing the rate of RAO. A recent meta-analysis documented a 68% reduction in the relative risk ratio (RRR) of RAO at 24 hours with RDA and 64% RRR of RAO at longer follow-up. (10) In addition, a reduction in local complications, mainly hematomas, has been reported. However, the need to change vascular access is greater with the RDA. At present, there is no evidence to support that the RDA is superior or non-inferior to the CRA in relation to the rate of net adverse clinical events in patients with STEMI receiving interventional treatment. This aspect should be studied in order to determine the place that the RDA should occupy in the context of interventional treatment for STEMI.

### **JUSTIFICATION**

Compared to femoral access, CRA is associated with a lower rate of adverse cardiovascular events and a lower incidence of vascular complications related to vascular access, mainly hemorrhagic. (4-6, 8) As of 2018 the European Society of Cardiology recommends RA as the access of choice in patients with ACS and as of 2021 the ACC/AHA for coronary interventions in patients with ACS. (1, 2) The most important complication of CRA is RAO, which, according to the latest good practice recommendations should not exceed 5%. (12) Advances in the technological development of hydrophilic and low-profile introducers have managed to reduce the RAO rate. However, the use of hemostasis with classic permeable radial artery, facilitated by or with compression of the ulnar artery, is the most important method that has reduced the RAO rate at 24 hours and at 30 days when CRA is used. (13) On the other hand, the optimal method of anticoagulation when radial access is used has not yet been defined, considering that the use of systemic anticoagulation is essential for the performance of PCI. (12)

**SALUD**  
SECRETARÍA DE SALUD

**Instituto Nacional de Cardiología Ignacio Chávez**  
*Renacimiento de la Excelencia*

One of the strongest pieces of evidence that has reduced the rate of proximal RAO from 8.4% to 0.7% at 24 hours is the use of the DRA. (11) A recent meta-analysis of randomized studies comparing CRA versus DRA documented a relative risk reduction of 68% for in-hospital RAO when using RDA. (10)

Randomized experimental studies have shown that the RDA does not increase the rate of RAO, in addition to offering advantages such as a lower bleeding rate and shorter hemostasis time compared to the CRA. (14) Therefore, it is essential to establish whether the benefit of the RDA in patients with ACS, particularly in patients with STEMI, is non-inferior to that which has been demonstrated with the CRA.

### **RESEARCH QUESTION**

Is the 30-day net adverse clinical event rate at 30 days in patients with STEMI undergoing PCI non-inferior when comparing DRA with CRA?

### **HYPOTHESIS**

H0: Is there a difference between the 30-day net adverse clinical event rates in patients with STEMI undergoing PCI when comparing DRA with CRA?

H1: The 30-day net adverse clinical event rate in patients with STEMI undergoing PCI is non-inferior when comparing DRA and CRA.

### **OBJECTIVES**

Primary:

The primary objective is to compare the composite of adverse events of all-cause mortality, AMI, cerebral vascular events, BARC type 3 or type 5 (Bleeding Academic Research Consortium) at 30 days in patients with STEMI who received PCI via RDA versus CRA.

Secondary:

**SALUD**  
SECRETARÍA DE SALUD

**Instituto Nacional de Cardiología Ignacio Chávez**

*Renacimiento de la Excelencia*

To compare the composite of net adverse events of all-cause mortality, AMI, cerebral vascular events, urgent Revascularization of Treated Vessel, definite stent thrombosis, type 3 or 5 BARC at 30 days evolution in patients with STEMI who received PCI via RDA versus CRA.

To compare the rate of clinical adverse events individually at 30 days of evolution in patients with STEMI who received PCI via RDA versus CRA.

## METHODOLOGY

Study design:

Prospective: Because of the temporality.

Randomized: For the assignment of the intervention.

Comparative: For the type of analysis.

Multicenter: Participation of 5 centers for patient recruitment.

\*Five centers in Mexico will participate, including the National Institute of Cardiology.

Description of the study population

Target population:

Patients with a diagnosis of STEMI who underwent PCI.

Eligible population:

Patients >18 years old, of both genders, with the diagnosis of STEMI undergoing PCI via RDA and CRA who are not in cardiogenic shock and have not previously undergone coronary revascularization surgical treatment.

Inclusion criteria:

**SALUD**  
SECRETARÍA DE SALUD

**Instituto Nacional de Cardiología Ignacio Chávez**  
*Renacimiento de la Excelencia*

Patients > 18 years old, with a diagnosis of STEMI undergoing PCI treatment at the Instituto Nacional de Cardiología Ignacio Chávez.

Patients with permeable radial artery in its proximal and distal segments.

Patients who agree to participate in the study and sign the informed consent form.

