#### Exclusion Criteria:

Patients meeting cardiogenic shock criteria, with a history of previous coronary revascularization surgery, and patients with absent radial pulse, carriers of AV fistula for hemodialysis or history of RAO will be excluded.

Patients who do not wish to enter the protocol or sign the informed consent form will also be excluded.

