#### Sample size:

The significance level (Alpha) will be 5%, power (1-beta) 80%. The composite major adverse event rate (all-cause mortality, AMI, cerebral vascular event, BARC type 3 or type 5) in the CR group was set at 4.19% based on the RIVAL study and with a non-inferiority cutoff of 1.89%. In the presence of a true difference in favor of the experimental group of 1.89%, the total population required is 2782 and 1391 patients per group to be 90% certain that the upper limit of the one-sided 95% confidence interval will exclude a difference in favor of the standard group of > 1.89%. The calculation of the final overall population with a 5% loss is 2922, 1461 patients per group.

In the Cath-lab at the Instituto Nacional de Cardiología Ignacio Chávez, 4608 procedures are performed per year, of which 3600 are in adults with ischemic and structural heart disease. Of this total group, 2880 are PCI. Approximately 90 procedures per month or 1080 per year correspond to patients with SICA; of these patients, approximately 65% (702) correspond to STEMI; thus, at least our institute would contribute 2106 patients for this multicenter study, which corresponds to 75% of the total population required; the rest of the centers should only contribute 766 patients. It is feasible to carry out the study over a period of 36 months.

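### The first inclusion criterion admits only patients treated at the lead institute, although the plan recruits at five centres; the forecast split between centres also does not add up

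*Combined protocol and SAP*

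**What the plan says.** Under Methodology, the study design entry reads "Multicenter: Participation of 5 centers for patient recruitment", and a footnote adds "Five centers in Mexico will participate, including the National Institute of Cardiology". The paragraph on the eligible population describes adults "with the diagnosis of STEMI undergoing PCI via RDA and CRA who are not in cardiogenic shock" and without previous bypass surgery; it names no site.

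The list headed Inclusion criteria then opens with patients over 18 "with a diagnosis of STEMI undergoing PCI treatment at the Instituto Nacional de Cardiología", giving the lead institute's full name. The exclusion criteria remove patients in cardiogenic shock, those with prior coronary bypass surgery, an absent radial pulse, an AV fistula for haemodialysis or a previous radial occlusion, and add "Patients who do not wish to enter the protocol or sign the informed consent form will also be excluded".

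The Sample size section states "the total population required is 2782 and 1391 patients per group" and, after an allowance for losses, "The calculation of the final overall population with a 5% loss is 2922, 1461 patients per group". For feasibility it gives about 90 ACS procedures a month at the institute, or 1080 a year, and "of these patients, approximately 65% (702) correspond to STEMI". From this it derives at least 2106 patients from the institute, described as 75% of the total required, leaves 766 to the other centres, and judges 36 months feasible.

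**The concern.** The inclusion list is the operative eligibility rule, and its first entry cannot be met by a patient treated at any of the other four centres. That contradicts the study design, the eligible population and the recruitment forecast in the same document. If sites and monitors apply the list literally, each enrolment outside the lead institute fails a stated criterion and becomes an eligibility deviation, although the rest of the plan means to enrol that patient.

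The recruitment forecast has a smaller defect that also concerns the other centres. The two contributions do not sum to either stated total, so the number expected from those centres is unclear.

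**Working it through.** **The site restriction.** The relevant statements side by side:

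| Place | Sites covered |
|---|---|
| Study design | Five centres, the lead institute being one |
| Eligible population | No site limit |
| Inclusion criteria, first entry | Lead institute only |
| Sample size, feasibility paragraph | Lead institute plus other centres |

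The institute's name also appears as page letterhead, so a text-extraction artefact had to be considered. It is not one: the restriction is inside the criterion sentence. No other statement widens or overrides it.

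**Inputs, all from the Sample size section:** 90 ACS procedures per month; 65% STEMI; 36 months; 2106 from the institute; 766 from the other centres; totals of 2782 before losses and 2922 after.

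**Reproducing the plan's figures.**
- Institute: 90 × 12 = 1080 per year; 1080 × 0.65 = 702 STEMI per year; 702 × 3 = 2106. This agrees.
- Loss allowance: 1391 × 1.05 = 1460.55, rounded up to 1461 per group; 2 × 1461 = 2922. This agrees.

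**Patients the criterion would bar, taking 2106 as given.**
- On 2922: 2922 − 2106 = 816, and 816 / 2922 = 27.9%.
- On 2782: 2782 − 2106 = 676, and 676 / 2782 = 24.3%.

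So the institute alone, on its own forecast, falls short of both totals.

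**The split.** 2106 + 766 = 2872.

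| Base | Remainder after 2106 | Stated 766 differs by | Institute share |
|---|---|---|---|
| 2782 | 676 | +90 | 2106 / 2782 = 75.7% |
| 2922 | 816 | −50 | 2106 / 2922 = 72.1% |
| 2872 (implied by the split) | 766 | 0 | 2106 / 2872 = 73.3% |

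The stated 75% fits the 2782 base, as does the plan's phrase for the total required. On that base the remainder should be 676. The figure 766 may be a transposition of 676, but the document does not confirm it. If the four other centres shared equally, 816 would mean 204 each and 766 about 192 each (191.5).

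**What 2106 represents.** It is the institute's whole approximate three-year STEMI volume. Nothing is taken off for the plan's own exclusions, for the requirement of a patent proximal and distal radial artery, or for refusals.

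**The case against.** The strongest reply is that this is a wording slip and everyone can see what was meant. The five-centre design is stated twice, the feasibility paragraph repeats it, and the text is plainly written from the lead site's viewpoint. A reader of the whole document would hardly conclude that four centres may not enrol. The document also describes no monitoring or deviation handling, so the consequence is inferred. And 816 or 676 patients would actually be ineligible only if sites applied unintended wording.

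Most of this is fair. The intent is clear, the counts are remainders of a forecast rather than a measure of damage, and no loss of power or delay follows from them. But clear intent elsewhere does not change what an eligibility criterion says, and correcting it costs one phrase.

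On the split, it is right that 75% is an acceptable rounding of 75.7% on 2782. The 72.1% arises only when the base is moved to 2922. The definite error is therefore 766. Restating on 2922 is advisable because that is the number to be recruited, not because the 75% is wrong on its own base. The equal-share figures are illustrative, since the document gives no allocation by centre. The caution about 2106 cannot be quantified, because no exclusion or consent rate is given; it supports a note and nothing more.

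**Conclusion.** The concern holds. As written, the first inclusion criterion contradicts the five-centre design and bars patients at four of the five centres: 27.9% of the final 2922, or 24.3% of 2782, assuming the institute delivers exactly its forecast 2106. It is very probably residual single-centre wording, but it is an operative rule and should be corrected.

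The split is a minor arithmetic error in a feasibility remark that sets no enrolment target. It leaves the other centres' expected number at 676, 766 or 816 depending on how it is read. Neither point affects the sample size calculation or the analysis.

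**What to change.** - Reword the first inclusion criterion so that it covers PCI at any of the five participating centres.
- Restate the split on the final 2922: if 2106 is kept, 816 from the other centres and an institute share of 72%.
- Add a note that 2106 is the institute's whole approximate three-year STEMI volume before exclusions and refusals, so the forecast may be somewhat less favourable than it looks.

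The cost is one phrase in the criterion, plus two figures and a note in the feasibility paragraph. Sample size, endpoint, margin and analysis stay as they are.

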#### Exclusion Criteria:

Patients meeting cardiogenic shock criteria, with a history of previous coronary revascularization surgery, and patients with absent radial pulse, carriers of AV fistula for hemodialysis or history of RAO will be excluded.

Patients who do not wish to enter the protocol or sign the informed consent form will also be excluded.

#### Elimination criteria:

Patients who do not complete the 30-day follow-up and those who withdraw from the study by their own decision will be eliminated.

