## STATISTICAL ANALYSIS PLAN

The SPSS 2020 package will be used for the statistical analysis as described above. No interim analysis has been pre-specified. The analysis will be by treatment intention according to assignment. Categorical variables will be expressed as percentages, and continuous variables as means  $\pm$  standard deviation. To compare categorical variables, the chi-square test or Fisher's exact test will be used, and to compare continuous variables, the Student's t-test or Mann-Whitney U test will be used. Survival

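### The elimination rule conflicts with the intention-to-treat analysis and, as written, drops randomised patients together with primary events already observed

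*Combined protocol and SAP*

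**What the plan says.** Under Methodology, Elimination criteria: "Patients who do not complete the 30-day follow-up and those who withdraw from the study by their own decision will be eliminated". The plan does not say what such patients are eliminated from (further participation, the dataset or the analysis). It makes no exception for a patient who has already had a primary event.

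The Statistical Analysis Plan says: "The analysis will be by treatment intention according to assignment". It names no other analysis set. It plans Kaplan-Meier curves, but gives no censoring rule and does not tie the curves to the primary test.

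The primary objective is to "compare the composite of adverse events of all-cause mortality, AMI, cerebral vascular events, BARC type 3 or type 5" at 30 days, and the alternative hypothesis is one of non-inferiority. The Sample size section says the event rate "in the CR group was set at 4.19% based on the RIVAL study and with a non-inferiority cutoff of 1.89" percent. It then says "the total population required is 2782 and 1391 patients per group", and "The calculation of the final overall population with a 5% loss is 2922", or 1461 per group. The trial is open-label.

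**The concern.** Both triggers for elimination, incomplete follow-up and withdrawal, arise after assignment. Removing randomised patients for such reasons gives up the protection of randomisation, and is not intention to treat. It also loses data already in hand: bleeding, infarction and stroke can all occur in hospital, before a patient is lost or withdraws.

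The trial has one confirmatory comparison, an absolute difference tested against a narrow margin with few events. Two analysts following this plan could use different denominators and different event counts. The open-label design makes unequal withdrawal between arms possible, although nothing shows that it will occur. The bias could favour non-inferiority, cancel out or work against it.

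**Working it through.** **Inputs from the Sample size section.** Control rate 4.19%; margin 1.89 points; one-sided 5% level; 1391 per arm required; 1461 per arm after the loss allowance.

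**The plan's own figure.** With 4.19% in both arms, a true difference of zero and 80% power:

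n = (1.645 + 0.842)² × 2 × 0.0419 × 0.9581 / 0.0189² ≈ 1390 per arm, against 1391 stated.

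Loss allowance: 1391 × 1.05 = 1460.55, rounded up to 1461 per arm, or 2922 in total. The planned loss is therefore 1461 − 1391 = 70 per arm.

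**Power cost.** Power = Φ(0.0189 / √(2 × 0.0419 × 0.9581 / n) − 1.645).

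- n = 1391: Φ(2.488 − 1.645) = 80.0%
- n = 1461: Φ(2.550 − 1.645) = 81.7%, if 30-day status is known for everyone

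**Weight of one event.** At 4.19%, about 61 events are expected among 1461 patients. One event is 100/1461 = 0.068 points, or 3.6% of the margin.

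**Illustrative shift.** The documents give no event rate for lost patients, so the following are assumptions: 70 lost per arm; CRA losses have events at 4.19%; DRA losses at k times that; a fraction f of these events is seen before loss; lost patients with no observed event count as event-free.

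Observed events = f × k × 0.0419 × 70, with k = 1 for CRA. Shift = (DRA observed − CRA observed) / 1461. The three values in each cell are for f = 0.25 / 0.50 / 0.75.

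| k | DRA events | CRA events | Shift, points | Share of 1.89 |
|---|---|---|---|---|
| 2 | 1.47 / 2.93 / 4.40 | 0.73 / 1.47 / 2.20 | 0.05 / 0.10 / 0.15 | 3–8% |
| 3 | 2.20 / 4.40 / 6.60 | same | 0.10 / 0.20 / 0.30 | 5–16% |
| 5 | 3.67 / 7.33 / 11.00 | same | 0.20 / 0.40 / 0.60 | 11–32% |

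The shift is about zero if losses are alike in the two arms, and reverses sign if only CRA losses are informative.

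**Effect on the conclusion.** One-sided 95% Wald upper limit, difference + 1.645 × SE, DRA minus CRA:

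- Completers 58 v 58 of 1391: 0 + 1.645 × 0.758 = 1.25
- The same start with the largest shift, 69.0 v 60.2 of 1461: 0.60 + 1.645 × 0.761 = 1.85, still inside
- Completers 65 v 58 of 1391: 0.50 + 1.645 × 0.779 = 1.79, inside
- The same trial with 4 DRA and 1 CRA observed events restored, 69 v 59 of 1461: 0.68 + 1.645 × 0.757 = 1.93, outside

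**Type I error.** Put the truth at the margin (4.19% v 6.08%) and eliminate 5% of each arm. If eliminated patients carry a share s of the arm's events, the completers' rate is p(1 − s)/0.95. The shares are assumptions and cover all events in eliminated patients, observed or not.

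| Share of events, CRA / DRA | Type I error |
|---|---|
| 0% / 0% | 3.9% |
| 5% / 5% | 5.0% |
| 10% / 10% | 6.4% |
| 20% / 20% | 10.4% |
| 5% / 10% | 10.4% |

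Imbalance between arms is therefore not needed. Removing equal but excess shares of events shrinks the absolute difference being tested: with 10% in both arms, 3.97% v 5.76%, or 1.79 points instead of 1.89.

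**The case against.** The strongest reply is that elimination may mean only that participation ends. The rule sits among the population criteria, while the section that governs analysis states intention to treat without exception. The 5% loss allowance fits either reading, and Kaplan-Meier curves normally accommodate partial follow-up by censoring. All of this is fair, and the loss of observed events follows from the plain wording without being stated outright. It does not resolve the conflict: the curves have no censoring rule and are not the primary test, and on the milder reading the handling of unknown 30-day status is still unstated.

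The magnitudes also rest on assumption, and the boundary crossing starts from a chosen case. From 65 v 58, restoring 3 v 1 events gives 1.86 and 4 v 2 gives 1.87, both inside the margin, and every k = 2 case stays inside (largest 1.88). The larger k = 3 and k = 5 cases do cross. Counting lost patients as event-free is not the same as censoring: if loss is very early, the 4 v 1 case gives about 2.01 instead of 1.93. These points limit what the figures can show, but the defect does not depend on them.

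Consent pages are not available and may cover use of data after withdrawal; they would not cover loss to follow-up.

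**Conclusion.** The concern holds. As written, the elimination rule excludes randomised patients for post-assignment reasons and drops observed primary events, contrary to the stated intention-to-treat analysis. The conflict rests on the text alone.

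The size and direction of the bias cannot be determined from the documents. The shifts of 0.05 to 0.60 points (3–32% of the margin) depend on assumed loss patterns. They would not overturn a result with equal completers, but could overturn one near the margin. Power is a minor matter. The main problem is an undefined primary analysis set in the only confirmatory comparison, so the point must be fixed.

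**What to change.** Remove the elimination rule as an analysis exclusion and reconcile it with the Statistical Analysis Plan. State that:

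- all randomised patients are analysed in their assigned arm;
- events observed before loss or withdrawal are counted, as far as consent allows;
- a death before day 30 is a primary event and counts as completed follow-up (a clarification, since the present wording does not say so);
- unknown 30-day status is handled by a named rule, for example censoring at last contact, with the primary estimate and its confidence limit computed accordingly.

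A sensitivity analysis for unknown status, such as a tipping point, is advisable. It tests robustness but does not reveal the direction of bias, and events never observed remain uncertain whatever rule is chosen. A completers analysis may be kept as supportive.

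The cost is a few sentences, one extra analysis, and the recording of event and last-contact dates. The variable list does not name these dates, but the planned Kaplan-Meier curves already need them. The sample size does not change. The wording should be settled before outcome data are reviewed, so that the choice cannot be influenced by the results.
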